- Number of family members in close contact developing common cold symptoms after the patient all over the study period.
- **Safety**: Assessment of adverse event/incidents/ undesirable expected side effects throughout the study.

Indication:

Treatment of acute rhinitis in children 6-10 years old

Investigation Design:

Prospective, open label, observational study

Visit 1 (V1) – (Day 1): Screening/Inclusion

Information and provision of the information sheet to legal guardians and participants, consent and assent signatures, demographic data and medical history, ongoing medication, physical and clinical examination, inclusion/non-inclusion criteria, record of patient choice regarding Healsea® Children use.

D1-D10 (at home):

Daily completion of the electronic diary (WURSS-K, adverse events/incident/undesirable expected side effects and concomitant medications, contamination of relatives if applicable, Healsea® Children daily administration if applicable).

D5±2 (at home): Telephone call 1

Investigator/nurse call to review patient status and study progress, adverse event/incident/undesirable expected side effects and concomitant treatments.

Visit 2 (V2) – (Day 10±2): End of treatment

End of Healsea® Children nasal spray treatment if applicable, assessment of symptoms, diary review, reporting of adverse events/incident/undesirable expected side effects.

D11-D30±5 (at home):

Daily completion of the diary (Adverse event, concomitant medications, contamination of relatives if applicable, WURSS-K if applicable, until the subject feels not sick for two consecutive days).

D20±2 (at home): Telephone call 2

Investigator/nurse call to review patient status and study progress, adverse events and concomitant treatments.

Version: **2.0**; **08** Sep **2021** Page **16** of **61** Study Number: **LPH-2101**

	Visit 3 (V3) – (Day 30±2): End of study					
	Physical and clinical examination, diary review, reporting of adverse events and					
	concomitant treatments.					
Number of Subjects:	15 centers will be involved in this study. We plan to follow a cohort of 200					
	subjects . The recruitment will be competitive in both group, exposed to					
	Healsea® Children or not exposed to Healsea® Children. However, when 100					
	patients will be recruited in one group, the recruitment will be stopped in this					
Towart Downlotions	group but will continue in the other group until 100 patients to be enrolled.					

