- **Safety:** All adverse events and incidents will be listed, but only treatmentemergent adverse events/incidents (non-serious + serious)/ undesirable expected side effects will be summarized.

Two groups (called treatment groups) will be extracted from the cohort according to the treatment chosen by the patient.

Adverse events and incidents will be summarized by the number and percentage of patients (by treatment group), classified by System Organ Class and Preferred Term as defined by MedDRA dictionary.

For a given treatment group, a given adverse event will be counted treatment emergent only once per patient during the treatment period.

Frequency and percentage of patients with at least one reported adverse event/ incident/ expected side effect will be tabulated by System Organ Class and by treatment group.

Version: **2.0**; **08** Sep **2021** Page **19** of **61** Study Number: **LPH-2101**

3. Flow Chart

	ACUTE PHASE			FOLLOW-UP			
Visit name	Screening/Inclusion	At home	Telephone call	End of treatment	At home	Telephone call	End of study
Visit Number	V1		TC1	V2		TC2	V3
Days/Weeks	D1	D1 – D10	D5±2	D10±2	D11 – D30±5	D20±2	D30 ± 5
Screening and General Assessments							
Information and consent process	Х						
Eligibility criteria	Х						
Demography and Medical history	Х						
Physical and clinical examination	X			Х			Х
Ongoing medication	Х						
Patient's choice for using Healsea® Children self-administration or not	Х						
Treatment							
Acute phase (Healsea® Children or no saline irrigation as add on therapy)		Х					
Assessments							
Subject e-diary (WURSS-K)		Х			X*		
Adverse Events/incidents/undesirable expected side effects and concomitant medication reporting	Х	Х	Х	Х	х	х	Х

^{*} After D10, the WURSS-K will be assessed once daily until the subject feels not sick for two consecutive days if applicable.

Version: **2.0; 08 Sep 2021** Study Number: **LPH-2101**

4. Identification and description of the investigational Device

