8.3.11 Study procedures

The study will comprise 3 visits and 2 telephone calls.

Version: **2.0**; **08** Sep **2021** Page **34** of **61**

Visit 1 (V1) - (Day 1): Screening/Inclusion

The investigator will give oral information relative to the study to parents/legal guardians and the participant. If both parents/legal guardians agree that their child participate in the study, they will receive the information sheet and will be also asked to give a written consent. In case one parent will not be available for the visit; he/she will be asked to confirm in writing that he/she agrees with the participation of the child in the study. Children will also receive an information specific to their age and will be invited to sign an assent by the investigator.

Each screened subject will be assigned a subject identifier number during screening. The subject identifier number will contain the site number and the subject number and will be assigned in numerical order at the screening visit based on chronological order of screening dates (e.g., 01-010 for the 10th subject screened at the Site #01).

The investigator or his/her delegated designee will:

- Record demographic data and medical history and ongoing medication,
- Perform a physical and clinical examination,
- Record the score of the common cold symptoms (headache, muscle ache, chilliness, sore throat, blocked nose, runny nose, cough, sneezing according a physician-rated symptom score after clinical examination of the child; (scale: 0 3 [0: no symptom, 1 = mild symptoms (sign/symptom clearly present, but minimal awareness; easily tolerated), 2 = moderate symptoms (definite awareness of sign/symptom that is bothersome but tolerable), 3 = severe symptoms (sign/symptom that is hard to tolerate; causes interference with activities of daily living and/or sleeping]). This scoring system was developed by Jackson in 1958 and is widely used in common cold clinical trials [19],
- Verify that eligibility criteria are fulfilled,
- Record the patient choice regarding Healsea® Children use (if the patient/parents choose nasal symptoms to be treated with Healsea® Children, instructions will be given to the patient/parents for getting the test product at the end of the visit),
- Explain to the child/parents/legal guardians how to use Healsea® Children if applicable,
- Review and detail the questions of the WURSS-K,
- Explain how to use the e-diary for WURSS-K recording, how to report adverse events/

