9.2 Study population

The study population consists in all the patients included and who do not meet a "major deviation to protocol" as defined in section 12.

The safety population consists in all the patients included in this study.

Version: **2.0**; **08 Sep 2021** Page **38** of **61**

The analysis of primary and secondary endpoints will be performed on study population, safety endpoint will be performed on safety population.

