2.2. Secondary objectives

The secondary objectives are:

- To assess the impact of both treatment modalities to reduce the duration of each infectious rhinitis symptom as rated by the Wisconsin Upper Respiratory Symptom Survey for Kids (WURSS-K).
- To assess the impact of both treatment modalities to reduce complications of the acute phase during a 20-day follow-up phase.
- To assess the impact of both treatment modalities on the intake of conventional common cold medication (antibiotics, antipyretics, mucolytics, decongestants, antitussives, systemic and topical corticosteroids).
- To assess the impact of both treatment modalities to reduce the person to person spreading among close contacts (parents, siblings).
- Safety: to assess systemic and local tolerance of Healsea® Children over the study period.

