5. DEFINITION OF THE ANALYSIS SETS

Screened subjects: all subjects who signed an informed consent.

Included subjects: all screened subjects who participated in the study.

Full Analysis Set (FAS): all included subjects who used the investigational medical device at least once.

Per-Protocol (PP) Set: Efficacy population based on the FAS without patients with major protocol deviations.

Safety and Efficacy analyses will be performed on the FAS.

The analyses of the primary and one secondary (modelling of AUC on total WURSS by multivariate ANCOVA) efficacy criteria will also be performed on the PP Set.

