11. SAFETY

The following analyses will be performed on the FAS.

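### Neither document assigns safety columns by actual use and their safety sets conflict, so device events can fall in the wrong column if a child's use differs from the recorded choice

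*Protocol*

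**What the plan says.** The safety objective concerns the device itself: "to assess systemic and local tolerance of Healsea® Children over the study period" (SAP 2.2, matching protocol 7.3).

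**Protocol.** The safety text in the synopsis, repeated in 9.5, states: "Two groups (called treatment groups) will be extracted from the cohort according to the treatment chosen by the patient". The choice is taken once, since the Visit 1 task list in 8.3.11 includes "Record the patient choice regarding Healsea® Children use". Section 9.2 adds: "The safety population consists in all the patients included in this study". Among the daily diary entries for D1-D10 the synopsis lists "Healsea® Children daily administration if applicable".

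**SAP.** Section 5 defines the Full Analysis Set (FAS) as "all included subjects who used the investigational medical device at least once" and continues: "Safety and Efficacy analyses will be performed on the FAS". Section 11 repeats: "The following analyses will be performed on the FAS". The efficacy sections (10.2.1 to 10.2.5) speak of the treatment chosen, but 11.2 does not say how children are placed in columns. The mock tables in 13.2 for non-related adverse events and for incidents nevertheless have Healsea Children, Conventional therapy and Total columns.

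Neither document has a rule for tabulating by actual use, or for a child whose use departs from the recorded choice.

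**The concern.** Only a child who uses the spray can show how well it is tolerated. Grouping by choice is defensible for efficacy, but for tolerance it can mislabel exposure in two ways. A child who chose Healsea and never sprayed adds to the Healsea denominator without being at risk of a device effect. A child who chose conventional therapy and later used the spray, which is CE-marked, carries any device effect into the conventional column. Both errors pull the columns together, which is the unfavourable direction for a tolerance summary. The effect most open to this is the only one that protocol 6.2 anticipates: nasal itching and irritation at the start of treatment.

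The two safety sets make this harder to resolve. The protocol keeps everyone; the SAP keeps users only. An analyst following the SAP to the letter would find almost nobody to put in the second column of the shells.

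**Working it through.** **The plan's own figure.** The documents give no safety rate to reproduce. The group size used below, 100 per group, is the planned one (protocol 7.4, SAP 4). It reproduces for an effect size of 0.4, 80% power and two-sided 5%: 99 per group by the normal formula (power at 100 is 80.7%) and 99.1, rounded up to 100, by the t-test (power 80.4%). The point does not depend on it.

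**The rules side by side.**

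| | Protocol (synopsis, 9.2, 9.5) | SAP (5, 11, 13.2) |
|---|---|---|
| Safety set | all included children | included children with at least one use |
| Column rule | treatment chosen | not stated |
| Healsea chooser, never sprays | Healsea column | not in the set |
| Conventional chooser, uses spray | conventional column | in the set, column not defined |
| Conventional chooser, never uses spray | conventional column | not in the set, read literally |

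**Size under the protocol set.** Let p be the event rate in users, with rate 0 in non-users; u the share of Healsea choosers who never use it; and c the share of conventional choosers who do. Then:

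- Healsea column: p(1 − u)
- Conventional column: p × c
- Difference: p(1 − u − c), against a true difference of p

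All rates here are assumptions. With p = 10% and 100 per group:

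| u = c | Healsea | Conventional | Difference (points) | Factor | Expected device cases under conventional |
|---|---|---|---|---|---|
| 0% | 10.0% | 0.0% | 10.0 | 1.00 | 0 |
| 5% | 9.5% | 0.5% | 9.0 | 0.90 | 0.5 |
| 10% | 9.0% | 1.0% | 8.0 | 0.80 | 1.0 |
| 20% | 8.0% | 2.0% | 6.0 | 0.60 | 2.0 |

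A 1% background rate leaves the factor unchanged: at 5% each the difference is 8.1 points against a true 9.0, which is 0.90.

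**Size under the SAP set.** Never-users drop out, so u = 0 and the Healsea column shows p. Two readings remain for the other column, taking crossover users to stay under their choice.

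- *Conventional children are kept in spite of the definition.* The factor is 1 − c: 0.95, 0.90 and 0.80 at c = 5%, 10% and 20%.
- *The definition is applied literally.* The conventional column holds 100 × c children: 0, 5, 10 or 20 at c = 0%, 5%, 10% or 20%. All of them are users, so both columns estimate p and their difference says nothing about the device.

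**The case against.** The case on the other side has real weight.

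- **The protocol leaves analysis details to the SAP, and the SAP removes never-users.** This stands. A reader might infer that a true 20% against 0% would be shown as 18% against 2% at 10% non-use and 10% crossover. That holds only for the protocol set. Under the SAP set the Healsea column stays at 20%.
- **The SAP does not adopt grouping by choice for safety.** This stands. A reader might infer that both documents group safety by choice; the SAP is silent, which is a gap and not the same rule.
- **Crossover is speculative.** Largely right. The listed major deviation concerns nasal irrigation, not Healsea, and under protocol 8.3.11 only families choosing Healsea are told how to obtain it. The documents make crossover possible; they do not predict it.
- **Use in comparator children is not invisible.** Every child's diary records concomitant medication, reviewed at both calls and validated at Visits 2 and 3. Capture is less systematic than a direct question, but not absent.
- **Related events are selected by causality and can be traced.** SAP 11.2 counts events judged other than unrelated, and Listing 16.2.7.1 covers all events. This helps only in part. The summary table would still show the event in the wrong column, and the dedicated incident listings cover only serious events and those leading to discontinuation. If spray use goes unrecorded, an event may be judged unrelated and pass to SAP 10.4, where the column is the only link to exposure.
- **The tables are descriptive.** Section 11.2 plans no test, and SAP 6.3.1 treats everything beyond the primary criterion as descriptive. The cost is therefore a misplaced count, not a false test result.

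**Conclusion.** The point holds as a conditional gap joined to a documented conflict. The conflict is certain: the protocol's safety set is all included children, the SAP's is device users, and the SAP shells need a conventional column that its own definition leaves empty apart from crossover users. The missing as-used rule is also certain. Misplaced or diluted events follow only if some child's use differs from the choice at Visit 1.

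A reader might conclude that device effects *are* diluted in this trial. The documents do not support that, because they give no rate of non-use or crossover, and with both at zero the difference is intact. On assumed rates of 5% to 10% in each direction, the protocol set keeps 0.90 to 0.80 of the risk difference. At a 10% event rate in users, that crossover would put 0.5 to 1.0 expected device cases per 100 children under conventional therapy. This is modest, but worth correcting because the correction is cheap.

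**What to change.** 1. Reconcile protocol 9.2 with SAP 5 and 11 by using one safety set of all included children.
2. In the protocol synopsis and 9.5, and in SAP 10.4 and 11.2, tabulate safety by actual exposure: at least one recorded Healsea use against none, taken from the diary and the concomitant-medication records. State how a child without any diary entry is classed.
3. List every child whose exposure differs from the recorded choice.
4. Keep grouping by choice for efficacy.

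The cost is wording and a derived variable. The data are already in the planned Listings 16.2.5.2 (daily administration) and 16.2.6.2 (medications). SAP 12 describes diary answers already seen, so data collection was probably under way when it was written; the tabulation rule can still be applied. The downside is that safety and efficacy column totals may differ by a few children, which a footnote can explain.

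Opening the daily Healsea-use item to comparator children would improve capture but is optional. In an open-label study based on family choice, asking about the product every day might prompt its use, and the change may come too late.

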4.1 Summary description of the investigational device

4.1.1 Summary description

Healsea® Children is a CE marked nasal spray composed with an isotonic seawater solution (0.9% NaCl) and Symbiofilm® (0.02%). Symbiofilm® is a Lallemand proprietary marine postbiotic composition including an exopolysaccharide mainly composed of N-acetyl hexosamines, acidic and neutral monosaccharides.

The sponsor certifies that the Healsea® Children Medical Device:

- does not contain any human blood derivative,
- does not contain any medicinal product,
- is not manufactured using tissues of animal origin.

Healsea® Children is a nasal spray indicated in children above 6 years to clean and moisten the nose during colds and rhinitis. Healsea® Children is administered with the help of an adult for colds and rhinitis, one puff (1-2 sec) twice a day in each nostril for 10 days.

The technical performances are summarized below:

Ingredient	Function(s)		
Isotonic Seawater solution 0.9%	- Improve nasal mucosa function		
	- Clean the nasal cavity and eliminate allergens		
	and infectious agents		
Symbiofilm	- Enhancing the cleansing efficacy		
	- Reducing biofilm formation		

Intended clinical performances in the intended destination are:

- Cleans and moistens the nose during colds and rhinitis.
- Cleans the nasal cavity and eliminates allergens and infectious agents.

4.2 Manufacturer

Healsea® Children is a Class IIa Medical Device manufactured by Lallemand Pharma. CE marking has been obtained on 30th of March 2021. The subcontractor for the manufacturing is AURENA, [name].

Version: **2.0**; **08** Sep **2021** Page **21** of **61**

4.3 Name or number of the model to permit full identification

The test device is named Healsea® Children. It is a nasal spray (100ml presentation), isotonic seawater (0.9%) supplemented with Symbiofilm® (0.02%) identified by the code article: 7640149724004.

4.4 Traceability

Traceability of the Device will be achieved through the lot number (YYMMXXX, YY for year, MM for Month and XXX internal number of the manufacturer), the manufacturing date (YYYY/MM/DD) and the expiry date (YYYY/MM/DD).

4.5 Intended purpose of the investigational device in the clinical investigation.

This is an observational study. Healsea® Children will be used in the paediatric IgE-dependent allergic population that is more prone to common cold and represents a suitable target for Healsea® Children.

Healsea® Children will be used within its intended purpose i.e., in children above 6 years to clean and moisten the nose during colds and rhinitis.

4.6 Population and indications for which the device is intended

Healsea® Children is a nasal spray indicated in children above 6 years to clean and moisten the nose during colds and rhinitis. Healsea® Children is administered with the help of an adult for colds and rhinitis, one puff (1-2 sec) twice a day in each nostril for 10 days.

[figure not shown]
4.7 Device Description

Healsea® Rescue is a nasal spray (available in 100mL) using the Bag-on-Valve (BoV) technology.

The BoV technology consists of an aerosol valve with a welded bag. The product is placed inside the bag while the propellant is filled in the space between bag and can. The product is dispensed by the propellant simply squeezing the bag when the spray button is pressed, the product is squeezed out of the bag by the compressed air/nitrogen, which creates the dispensing as a spray. Therefore, the product keeps its integrity, remaining separated from the propellant at all times. Compared to traditional aerosol spray technology, BoV has several benefits, for manufacturers, consumers and the environment. Packaging description of Healsea Children is reported in Figure 1.

Version: **2.0**; **08** Sep **2021** Page **22** of **61**

*Packaging element in contact with the product

Figure SEQ Figure * ARABIC 1- Packaging description of Healsea® Children

As summarized below, Healsea® Children is intended to be used on nasal mucosa. The duration of use is 10 days.

Table 1 : Device Category / Intended Use

Type of contact	Device in contact with a surface
Type of tissues	Mucous membranes
Total duration treatment	It can be used for 10 days

4.8 Investigation Device Training/Experience

There is no need for specific training in using Healsea® Children.

A usability engineering process test according to the standard EN ISO 62366-1: 2015 was conducted with Healsea® Children with 10 people representative of the parents/legal guardians of the target population to ensure that the leaflet and the label were well understood, and that the medical device was used correctly to ensure its safe understanding and use.

The analysis of the results demonstrates that:

- The information provided by the user interface is readable and understandable by participants: the information tested was easy to understand, without interpretation.
- The observations made during the simulations of use of the device have confirmed that all safety-related handling steps are properly followed, in accordance with the instructions given in the instruction for use.

Briefly, the children (with the help of an adult if necessary) to place the nozzle into the nostril while keeping head straight. Once the nozzle is placed, to press on the nozzle for 1-2 seconds in each nostril. To let flow the excess of solution, and wipe. To clean the nozzle with tissue, soapy water rinse and dry after use.

4.9 Reference to the IFU

The IFU of Healsea® Children is provided in Appendix A.

5. Justification for the design of the clinical investigation

Although clinical evidence from well-designed trials is scarce [1], European guidelines for acute rhinitis/rhinosinusitis recommend daily nasal saline irrigation for reduction of the severity of symptoms and for speeding recovery [2]. The exact mechanisms by which nasal irrigation works are

Version: **2.0**; **08** Sep **2021** Page **24** of **61**

not known. However, most of the experts agree that it is primarily a mechanical intervention leading to direct cleaning of the nasal mucosa [3] [4]. The mucus lining the nasal cavity may be softened and dislodged. The increase of mucociliary clearance is associated with a decrease of pathogens burden. Moreover, inflammatory mediators such as cytokines, prostaglandins and leukotrienes can be removed, favoring the resolution of URTIs. Nevertheless, the efficacy of such saline irrigation remains moderate [1].

Symbiofilm® is an exopolysaccharide composition with emulsifying properties and *in vitro* antibiofilm activity. Antibiofilm properties have been demonstrated with a microtiter plate assay [5]. In both models, a significant inhibition of *Staphylococcus aureus* and *Haemophilus influenzae* biofilms was observed. Detachment properties from human nasal epithelial cells of *Staphylococcus aureus* and *Pseudomonas aeruginosa* has also been demonstrated *in vitro*, suggesting an inhibition of biofilm formation at early stage in this model. The antibiofilm activity of Symbiofilm® is likely to rely on its emulsifying properties. In all models, the absence of bacteriostatic or bactericidal activities against all strains tested has been confirmed.

The technical performances of Symbiofilm® may enhance the interest of saline nasal irrigation for the treatment of acute infectious rhinitis and common cold.

The common cold is the most frequent upper respiratory tract infection (URTI), which is the most commonly treated acute problem in primary pediatric care [6]. Despite the usually benign nature of the illness, the common cold is an enormous economic burden on society in terms of visits to doctors, treatments, and absences from work, school, or day care [6][7]. The common cold is an acute viral infection of the upper respiratory tract, involving, to variable degrees, sneezing, nasal congestion and discharge (rhinorrhea), sore throat, cough, low-grade fever, headache, and malaise [2]. It can be caused by members of several families of viruses. However, rhinoviruses have been consistently found to be the most common cause in all age groups, irrespective of the viral detection techniques used. Yearly, rhinoviruses account for about 30-50% of all respiratory illnesses, but during the autumn peak season these viruses can cause up to 80% of all upper respiratory infections. Coronaviruses and Influenza viruses account for about 10-15% and for 5-15% of acute infectious rhinitis respectively. Other viruses such as Respiratory Syncytial Virus, Adenoviruses and Parainfluenza viruses are less involved [7]. Acute viral rhinitis is generally self-limiting. In children where the illness is not self-limiting and extends beyond 7-10 days, many agree that a bacterial infection is likely [2]. Acute bacterial rhinosinusitis is diagnosed in a child based on several criteria: persistent upper respiratory tract symptoms more than 10 days (cough or nasal discharge or both); or recurrence of symptoms after initial improvement: fever, worsening cough, or worsening or new purulent rhinorrhea; or severe onset of symptoms like fever or purulent nasal discharge lasting more than three consecutive days associated with facial tenderness or headache. Bacterial over infections and progression to a chronic condition are favored by the formation of biofilms, which facilitate bacterial growth and persistence as well as reducing antibiotic efficacy [8][9].

Allergic diseases may play a particular role in promoting the respiratory infection recurrences. The physiological immune response is impaired in allergic subjects and allergic inflammation favours predisposition to respiratory infections [10]. Subjects with allergic disorders may have functional defect of type 1 immune response that is relevant in fighting infections [11][12]. Allergic rhinitis (AR)

Version: **2.0**; **08** Sep **2021** Page **25** of **61**

may affect up to 40% of the paediatric population. Nasal symptoms are caused by exposure to an allergen to which a patient is sensitized. Typical allergens include house dust mite, grass pollen, tree pollen, weed pollens, cat, dog and moulds. Allergic rhinitis can thus be seasonal or perennial, according to the relevant allergen. AR is characterized by typical nasal symptoms and IgE-mediated inflammation. The allergic inflammatory process releases many cytokines and other proinflammatory proteins. Inflammation caused by nasal allergy leads to obstruction, fluid accumulation and acute disease. If these diseases are unsuccessfully treated, a chronic status of inflammation, obstruction, and infection develops that can cause mucosal damage and, ultimately, chronic disease [14].

For these reasons, the paediatric IgE-dependent allergic population that is more prone to common cold represents a suitable target for Healsea® Children [15][16]. During this prospective observational study, one cohort of IgE-dependent allergic children with early symptoms of infectious rhinitis will be followed, children being treated with Healsea® Children on top of common cold conventional therapies or with conventional therapies only (excluded nasal irrigation). Conventional therapies for non-complicated infectious rhinitis are symptomatic but are not without side effects [17][6]. For example, decongestant use can increase blood pressure, antihistamine intake is associated with drowsiness that can not only improve acute infectious rhinitis symptomatology but could also limit the complication and progression to chronic state.

This observational study aimed to confirm the benefit of Healsea® Children in a real life setting in children with perennial allergy.

6. Risks and Benefits of the Investigational Device and Clinical Investigation

